7.2. Laboratory Evaluations

Laboratory data collected during the study will be analyzed and summarized using both quantitative and qualitative methods. Summaries of laboratory data will be provided for the Safety Analysis Set and will include data collected up to the last dose of study drug plus 30 days for subjects who have permanently discontinued study drug. The analysis will be based on values reported in conventional units. When values are below the LOQ, they will be listed as such, and the closest imputed value will be used for the purpose of calculating summary statistics as specified in Section 3.7. Hemolyzed test results will not be included in the analysis, but they will be listed in by-subject laboratory listings.

A by-subject listing for laboratory test results will be provided by subject ID number and time point in chronological order for hematology, serum chemistry, and urinalysis separately. Values falling outside of the relevant reference range and/or having a severity grade of 1 or higher on the CTCAE severity grade will be flagged in the data listings, as appropriate.

No formal statistical testing is planned.

7.2.1. Summaries of Numeric Laboratory Results

Descriptive statistics for laboratory tests will not be provided.

7.2.2. Graded Laboratory Values

The CTCAE Version 5.0 will be used to assign toxicity grades (0 to 4) to laboratory results for analysis. Grade 0 includes all values that do not meet the criteria for an abnormality of at least Grade 1. For laboratory tests with criteria for both increased and decreased levels, analyses for each direction (i.e., increased, decreased) will be presented separately.

7.2.2.1. Treatment-Emergent Laboratory Abnormalities

Treatment-emergent laboratory abnormalities for Blinded Treatment phase are defined as values that increase at least 1 toxicity grade from baseline at any postbaseline time point,

- up to and including the date of last dose of Blinded Treatment phase study drug plus 30 days for subjects who permanently discontinued Blinded Treatment phase study drug
- or before the first dose of OL Treatment phase study drug for subjects who entered OL Treatment phase

For subjects who entered the OL Treatment phase, treatment-emergent laboratory abnormalities for OL Treatment phase are defined as values that increase at least 1 toxicity grade from OL baseline at any postbaseline time point, up to and including the date of last dose of OL Treatment phase study drug plus 30 days for subjects who permanently discontinued OL phase study drug.

If the relevant baseline laboratory value is missing, any abnormality of at least Grade 1 observed within the time frame specified above will be considered treatment emergent.

7.2.2.2. Summaries of Laboratory Abnormalities

Laboratory data that are categorical will be summarized using the number and percentage of subjects in the study with the given response at baseline and each scheduled postbaseline time point for both Blinded Treatment phase and OL Treatment phase.

The following summary (number and percentage of subjects) for treatment-emergent laboratory abnormalities will be provided by laboratory test and treatment group; subjects will be categorized according to the most severe postbaseline abnormality grade for a given laboratory test:

- Graded laboratory abnormalities

For all summaries of laboratory abnormalities, the denominator is the number of subjects with nonmissing postbaseline values.

7.3. Body Weight and Vital Signs

Body weight and vital signs will not be summarized or listed.

7.4. Prior and Concomitant Medications

Medications collected at screening and during the study will be coded using the current version of the World Health Organization (WHO) Drug dictionary.

UC-specific prior and concomitant medications at baseline will be included in the listing of other baseline characteristics as described in Section 5.2. No other prior and concomitant medications will be summarized or listed.

7.4.1. Prior Medications

Prior medications are defined as any medications taken before a subject took the first study drug.

For the purposes of analysis, any UC-specific medication with a start date prior to the first dosing date of study drug will be included in the UC treatment history summary in the listing of other baseline characteristics as described in Section 5.2, regardless of when the stop date is. If a partial start date is entered the medication will be considered prior unless the month and year (if day is missing) or year (if day and month are missing) of the start date are after the first dosing date. Medications with a completely missing start date will be included in the UC treatment history summary, unless otherwise specified.

7.4.2. Concomitant Medications

Concomitant medications are defined as medications taken while a subject took study drug.

For the purposes of analysis, any UC-specific medications with a start date prior to or on the first dosing date of study drug and continued to be taken after the first dosing date, or started after the first dosing date but prior to or on the last dosing date of study drug will be considered concomitant medications. Medications started and stopped on the same day as the first dosing date or the last dosing date of study drug will also be considered concomitant. Medications with a stop date prior to the date of first dosing date of study drug or a start date after the last dosing date of study drug will be excluded from the UC concomitant medication summary in the listing of other baseline characteristics as described in Section 5.2. If a partial stop date is entered, any medication with the month and year (if day is missing) or year (if day and month are missing) prior to the date of first study drug administration will be excluded from the UC concomitant medication summary. If a partial start date is entered, any medication with the month and year (if day is missing) or year (if day and month are missing) after the study drug stop date will be excluded from the UC concomitant medication summary. Medications with completely missing start and stop dates will be included in the UC concomitant medication summary, unless otherwise specified.

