3.8. Analysis Visit Windows

3.8.1. Definition of Study Day

For all subjects who received at least 1 dose of study drug, Study Day will be calculated from the first dosing date of study drug and derived as follows:

- For postdose study days: Assessment Date – First Dosing Date + 1
- For days prior to the first dose: Assessment Date – First Dosing Date

Therefore, Study Day 1 is the day of first dose of study drug administration.

Baseline is defined as the last available observation on or prior to Study Day 1, unless otherwise specified.

For subjects who entered OL Treatment phase and received at least 1 dose of study drug (OL GS-4875), OL Study Day will be calculated from the first dosing date of study drug in OL Treatment phase and derived as follows:

- For postdose OL study days: Assessment Date – First Dosing Date of study drug in OL Treatment phase + 1

Therefore, OL (Study) Day 1 is the day of first dose of study drug administration in OL Treatment phase.

OL baseline is defined as the last available observation on or prior to OL Study Day 1, unless otherwise specified.

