5.2. Other Baseline Characteristics

The following baseline disease characteristics will be summarized by treatment group and overall using descriptive statistics for continuous variables and using number and percentage of subjects for categorical variables:

- Duration of UC (in years) from date of diagnosis to first dosing date
- MCS
- Partial MCS (pMCS)
- Endoscopic subscore of 3 (yes, no)

The summary of these baseline characteristics will be provided for the Safety Analysis Set. No formal statistical testing is planned.

A by-subject listing of baseline disease characteristics will be provided by subject ID number in ascending order. The following baseline disease characteristics will also be included in the listing:

- Extent of UC from medical history
- UC treatment history
 - Prior use of biologic agents (yes, no)
 - Number of TNF α antagonist used (1, 2, \geq 3)
 - Prior use of vedolizumab (yes, no)
 - Prior use of ustekinumab (yes, no)

- UC concomitant medication
 - Systemically absorbed corticosteroids (yes, no)

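### Could the baseline corticosteroid entry in the SAP's UC medication listing pick up drugs started on treatment, and does that need a change?

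*SAP*

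**What the plan says.** SAP 7.4 sets the scope of the output: "UC-specific prior and concomitant medications at baseline will be included in the listing of other baseline characteristics". It then closes the door on anything else: "No other prior and concomitant medications will be summarized or listed". SAP 5.2 places the steroid item among the baseline disease characteristics, under UC concomitant medication, as a yes/no with no reference date. It belongs to the second group of items in 5.2, which are listed by subject and not summarised. The general rule in SAP 3.8.1 is "Baseline is defined as the last available observation on or prior to Study Day 1, unless otherwise specified".

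SAP 7.4.2 classifies UC drugs by date. A drug is concomitant if it began by the day of first dose and was still in use later. The rule then goes on to cover later starts: "or started after the first dosing date but prior to or on the last dosing date of study drug will be considered concomitant medications". A drug started and stopped on the first dosing date, or started and stopped on the last, also counts. Drugs stopped before first dose or started after last dose "will be excluded from the UC concomitant medication summary in the listing of other baseline characteristics as described in Section 5.2". Partial dates have parallel rules; a drug whose partial start date falls "after the study drug stop date will be excluded from the UC concomitant medication summary".

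SAP 7.4.1 treats any UC drug started before first dose as prior, whatever its stop date. The treatment history items in 5.2 cover biologics, TNFα antagonists, vedolizumab and ustekinumab; none concerns steroids.

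**The concern.** Section 7.4.2 names the 5.2 listing and writes its own exclusions for it, and none of them removes a drug started after first dose. A programmer who codes 7.4.2 alone would show a yes for a subject who first took a steroid on, say, Day 30. A programmer who applies the baseline scope in 7.4 would show a no. The same data could therefore give two entries.

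There is also a hole in the date rules. A steroid begun before first dose and stopped on the first dosing date did not continue afterwards, did not start that day, and did not stop before it. The 7.4.2 date rules neither include nor exclude it, although it was in use at baseline.

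This could seem to matter because efficacy is reported only by subject (SAP 6.2.2 and 6.3.2), so a reader sees individual values and not averages. Protocol 5.4.1 also warns that changes in UC medication may confound the assessments. A value labelled baseline ought to be one.

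**Working it through.** No sample size or power figure is involved. The check sets the date rules against use at first dose.

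**Inputs.** The date rules come from SAP 7.4.2. Use at baseline is taken as started on or before the first dosing date and not stopped before it. A start or stop can fall in five positions: before first dose; on the first dosing date; between; on the last dosing date; after last dose or ongoing. First and last dosing dates are assumed to differ. With start no later than stop, there are 5 × 6 / 2 = 15 orders.

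| Start | Stop | SAP 7.4.2 | In use at first dose | Orders |
|---|---|---|---|---|
| on or before first dose | after first dose | concomitant | yes | 2 × 3 = 6 |
| first dosing date | same day | concomitant | yes | 1 |
| after first dose, up to last dose | any later or same position | concomitant | no | 3 + 2 = 5 |
| before first dose | before first dose | excluded | no | 1 |
| after last dose | after last dose or ongoing | excluded | no | 1 |
| before first dose | first dosing date | neither | yes | 1 |

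The rows sum to 6 + 1 + 5 + 1 + 1 + 1 = 15. The rules agree with baseline use in 6 + 1 + 1 + 1 = 9 orders, differ in 5, and are silent in 1.

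**What the count means.** The five discordant orders are one condition, a start after first dose and up to last dose, split by stop date. They are not five separate faults, and 5 of 15 is not a rate. The count is also per drug record, while the listing carries one yes/no per subject. A discordant record makes the entry wrong only if no other steroid record for that subject covers first dose.

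**Who could be affected.** The subject must be off steroids at first dose and start one on or before last dose. Protocol 5.4.1 and 6.13.3 say that starting a UC steroid, or raising it above the Day 1 dose, requires study drug to be discontinued. Medications are recorded at visits, which are nominally 28 days apart after Week 6 (for example 71 − 43 = 28), so a start could precede the last dose. That makes the case possible; it does not show that it occurred.

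A re-start after taper under Protocol 5.4.1.1 is different. It applies to subjects tapering from a Day 1 dose, so they were on steroids at baseline and a yes is correct on either reading.

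**The silent order.** The opening sentence of 7.4.2 defines concomitant as taken while study drug was taken, which arguably covers a steroid taken on the first dosing date. SAP 7.4.1 also makes it prior. Protocol 5.4.1 asks for stable doses of allowed UC drugs, with steroid taper only after the Week 10 visit, so a stop on Day 1 would be unusual.

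**Where the entry goes.** SAP 3.3 uses no covariates, 3.4 has no subgroups, 3.5 has no tests, and 6.2.2 and 6.3.2 drop the efficacy summaries. The steroid item enters no derivation of an endpoint in SAP 6.1.

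**The case for a change.** The best argument for a change is that reading 7.4 as a filter leaves parts of 7.4.2 idle. Two of its four exclusion rules, for a complete start date after last dose and a partial start date after study drug stopped, would have nothing left to remove. Under that reading, drugs started on treatment also appear in no medication listing, although Protocol 8.6.4 said individual concomitant medication data would be provided. A permitted steroid re-start need not surface as a deviation or a discontinuation, yet Mayo scores are still listed by visit. A few words and one short listing would settle all of this.

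Part of this stands. The three sections are not aligned, and 7.4.2 reads like general-purpose text carried into a shortened plan. But redundant exclusions do no harm: a drug started after last dose stays out either way. SAP 3.8.1 helps less than it seems, because it speaks of observations and not medication intervals; the scope statement in 7.4 and the heading of 5.2 are what decide the reading.

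The missing on-treatment listing is a disclosed reduction. SAP 7.4 says no other medications will be listed, and 7.7 says only part of the planned safety output will be produced. Discontinuation reasons (4.1), important deviations (4.3) and adverse event listings (7.1.6.1) remain, and the protocol still requires the medication data to be recorded. Taper follows the Week 10 response evaluation, so a later re-start cannot affect the Week 10 listings. It could bear on later scores, but the SAP plans no efficacy summary or test of them.

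**Conclusion.** The conflict in wording is real and minor, and it calls for no change to the plan. The title of 5.2 and the scope in 7.4 point to one sensible reading: the steroid entry means in use at first dose. An analyst can apply that reading to the discordant condition and to the one silent date pattern.

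The most that can go wrong is an individual yes/no in a by-subject listing among 19 enrolled subjects. No percentage, estimate or test depends on it. The documents do not show whether any subject started a steroid on treatment, or stopped one on Day 1, so the number of affected entries is unknown and could be zero.

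This rests on three assumptions: the entry stays listing-only, as SAP 5.2 has it; no analysis conditioned on baseline steroid use is added; and programmers read 7.4 together with 7.4.2. If the entry were later used to stratify or define a subgroup, its date definition would need to be written down first. A dated listing of on-treatment UC drugs would be a matter of preference in a synoptic report that openly omits such output.

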7.5. Electrocardiogram Results

Electrocardiogram (ECG) data will not be summarized or listed.

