2. OBJECTIVES AND ENDPOINTS

The objectives and associated endpoints of this study are presented in [Table 2-1](#).

Table 2-1. Objectives and Endpoints of Study GS-US-365-4237

Primary Objective	Primary Endpoint
To demonstrate the efficacy of GS-4875, compared with placebo control, in achieving Clinical Remission per Modified Mayo Clinic Score (MCS) at Week 10	Clinical Remission per Modified MCS, defined as Stool Frequency subscore ≤ 1 and not greater than baseline, Rectal Bleeding subscore of 0, and Endoscopic subscore ≤ 1 at Week 10
Key Secondary Objectives	Key Secondary Endpoints
To demonstrate the efficacy of GS-4875, compared with placebo control, in achieving endoscopic response at Week 10	Endoscopic Response, defined as an Endoscopic subscore ≤ 1 at Week 10
To demonstrate the efficacy of GS-4875, compared with placebo control, in achieving MCS Response at Week 10	MCS Response, defined as a decrease from baseline of ≥ 3 points and at least 30% in MCS, in addition to a ≥ 1 point decrease from baseline in the Rectal Bleeding subscore or a Rectal Bleeding subscore ≤ 1 at Week 10
To demonstrate the efficacy of GS-4875, compared with placebo control, in achieving MCS Remission at Week 10	MCS Remission, defined as a MCS score of ≤ 2 and no individual subscore > 1 at Week 10
To evaluate GS-4875, as compared with placebo control, in achieving histologic remission at Week 10	Histologic remission based upon the Geboes Scale where all of the following must be met at Week 10: Grade 0 of ≤ 0.3 , Grade 1 of ≤ 1.1 , Grade 2a of $\leq 2A.3$, Grade 2b of 2B.0, Grade 3 of 3.0, Grade 4 of 4.0, and Grade 5 of 5.0 (Appendix 5)
Other Secondary Objectives	Other Secondary Endpoints
To evaluate the safety and tolerability of GS-4875	Incidence and characterization of AEs and laboratory abnormalities
	Physical examination (PE) findings, electrocardiogram (ECG), and vital signs

[figure not shown]

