8.6.4. Other Safety Evaluations

Individual data for PE findings, prior and concomitant medications and medical history will be provided. Twelve-lead ECGs and vital signs measurements will be listed by subject and summarized by incidence of events/abnormalities or descriptive statistics as appropriate.

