Efficacy will be assessed primarily through modified MCS. MCS will be assessed at Screening, Blinded Treatment phase Week 10 and Week 50, and OL Treatment phase Week 10 and Week 50, if applicable.

Additional details on efficacy assessments are presented in Section 6, [Appendix 1](#), and [Appendix 2](#).

Safety will be assessed primarily through adverse events (AEs), laboratory analyses, electrocardiogram (ECG), physical examination (PE) and vital signs. Laboratory testing, PE and vital signs will be assessed at every visit.

Additional details on safety assessments are presented in Section 7, [Appendix 1](#) and [Appendix 2](#).

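### SAP 7.3 and 7.5 drop vital signs and ECG even from by-subject listings, although both belong to a protocol safety endpoint and Protocol 8.6.4 promises listings (minor)

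*SAP*

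**What the plan says.** Protocol Table 2-1 puts two endpoint lines under the safety and tolerability objective. One is "Incidence and characterization of AEs and laboratory abnormalities". The other is "Physical examination (PE) findings, electrocardiogram (ECG), and vital signs".

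Protocol 8.6.4 says how the second line is to be reported: "Twelve-lead ECGs and vital signs measurements will be listed by subject and summarized by incidence of events/abnormalities or descriptive statistics as appropriate". For physical examination (PE) and two other items it says: "Individual data for PE findings, prior and concomitant medications and medical history will be provided".

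The SAP was written after enrolment had been stopped at 19 subjects, to support a synoptic report. SAP 7.3 reads "Body weight and vital signs will not be summarized or listed" and SAP 7.5 reads "Electrocardiogram (ECG) data will not be summarized or listed". SAP 7.6 plans only a pregnancy listing, and no visible part of SAP Section 7 plans any PE output. SAP 7.7, the section for departures from the protocol's safety analyses, says in one general sentence that limited enrolment means only some of the planned safety output will be produced. It names none of the outputs that are lost.

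**The concern.** A protocol endpoint line has no planned table or listing for ECG or vital signs, and none that can be seen for PE. Limited enrolment is the stated reason. It justifies removing summary statistics and tests, which would say little with 19 subjects across three arms. It does not justify removing listings, because a by-subject listing is the natural format for so few subjects and needs no minimum sample size.

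At stake is whether changes in ECG or vital signs that never became adverse events can be seen in the report at all. Protocol 1.4 calls the drug first in class. Its first-in-human study dosed healthy subjects for up to 10 days, while Protocol 3.2 allows up to 60 weeks of treatment here. The planned safety reviews by the data monitoring committee were not held (SAP 2.1.2), so the report is the main place where these data would appear.

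**Working it through.** The plan states no figure on this point, so the check is a comparison of the two documents, followed by a count that bounds the size.

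**1. Protocol 8.6.4 against the SAP**

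| Item | Protocol 8.6.4 | SAP | Output left in the visible SAP |
|---|---|---|---|
| ECG | by-subject listing and summary | 7.5: neither | none |
| Vital signs | by-subject listing and summary | 7.3: neither | none |
| PE findings | individual data | not mentioned in visible Section 7 | none |
| Medical history | individual data | 5.3: extent of UC only | reduced |
| Prior and concomitant medication | individual data | 7.4: UC-specific items at baseline only | reduced |

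SAP 5.1 summarises baseline weight, height and BMI. This does not fill the vital-signs gap, because Protocol 6.9.3 defines vital signs as pulse, respiratory rate, blood pressure and temperature.

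**2. How the SAP treats other data with the same 19 subjects**

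- Primary and secondary efficacy (6.2.2, 6.3.2): summaries dropped, by-subject listings of status kept, except for histology, which will not be read.
- Laboratory data (7.2, 7.2.1): descriptive statistics dropped, by-subject listings kept.
- Adverse events (7.1.6.1): summaries and listings kept.
- Biomarkers (Section 9): by-subject listing kept.
- COVID-19 deviations (4.3): listed, including the non-important ones.

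The usual step is therefore to drop the summary and keep the listing. ECG and vital signs lose both.

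**3. What adverse event reporting still captures**

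Protocol 7.5 requires an abnormal ECG or vital-sign assessment to be recorded as an adverse event when it comes with signs or symptoms and meets the definition. Protocol 7.1.1 defines adverse events broadly. The remainder is change without symptoms that the investigator did not record as an event, for example a shift in QT or blood pressure.

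**4. Size of the listings, from the visit schedules**

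The number of records actually collected is not in the documents. The schedules (Protocol Appendices 2 and 3) give a ceiling, assuming no unscheduled visits and no early termination (ET) visit between the two phases. The longest path is a subject who enters the open-label phase at Week 10 and completes it.

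- ECG: Screening, Week 10, then open-label Weeks 10, 30 and 50 = 5 per subject. Ceiling 19 × 5 = 95 ECGs. An ET visit takes the place of a later scheduled visit and does not add to this.
- Vital signs, taken at every visit (Protocol 6.9.3): Screening (1) + Weeks 0, 2, 4, 6, 10 (5) + open-label visits (15) + posttreatment (1) = 22 per subject. Ceiling 19 × 22 = 418 visit rows.

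These bound the length of the listings. They do not measure how much information is lost.

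**5. Availability of the data**

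Protocol 6.9.4 has ECG results, with the investigator's interpretation, entered in the eCRF. SAP 4.2.1 already uses vital-sign assessment dates. Neither listing needs new collection. For PE, Protocol 6.9.3 says changes from screening are recorded, but describes the detail of the complete examination as source documentation, so it is not clear that PE findings are in the database.

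**The case against.** The strongest reply is that nothing is hidden. SAP 7.3 and 7.5 each state the cut under their own heading, 7.7 gives the reason, the SAP Introduction announces early termination and a synoptic report, and Protocol 9.2.2 allows an abbreviated report. The SAP also cuts elsewhere: histology is not read, other medical history and non-UC medications are not listed, and laboratory descriptive statistics are dropped. Which outputs a terminated study keeps is partly a reporting choice. This stands, and it rules out reading the change as undisclosed. It does not explain why listings are kept for laboratory data and biomarkers and not for ECG and vital signs.

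A reader might infer that the PE gap is as large as the other two. The documents do not support that. Protocol 6.9.3 has a complete examination only at screening and symptom-driven examinations at all other visits. A finding after first dose will therefore usually follow a reported sign or symptom, and all adverse events from that point are recorded and listed. What remains is that PE is left out without any statement.

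A reader might also take SAP 1.2 as contradicting Section 7, since it says "Safety will be assessed primarily through adverse events (AEs), laboratory analyses, electrocardiogram (ECG), physical examination (PE) and vital signs" and "Laboratory testing, PE and vital signs will be assessed at every visit". Those sentences sit under Study Design and describe what is assessed at visits. Collecting data and not tabulating it are compatible, so the wording is editorial.

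**Conclusion.** The point holds and is minor. The SAP openly removes ECG and vital signs from both summaries and listings, against a named protocol endpoint and a specific promise in Protocol 8.6.4. Limited enrolment supports the first removal and not the second.

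The loss is confined to ECG and vital-sign change not recorded as adverse events, in at most 19 subjects, and is probably small for PE. The figure is a maximum because SAP 3.7 allows for an enrolled subject who was never dosed. Adverse events, serious adverse events, deaths and graded laboratory abnormalities keep their output. No between-arm inference is affected, since the SAP makes none. It would be wrong to infer that the trial's safety reporting as a whole is missing or that a treatment comparison is biased.

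The conclusion rests on the visible SAP text, as redacted blocks cannot be checked. It also assumes that ECG and vital-sign records are in the database, as Protocol 6.9.4 and SAP 4.2.1 indicate.

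**What to change.** - **SAP 7.3:** replace the text with a by-subject listing of vital signs by subject ID and visit, on the All Randomized Analysis Set, which SAP 3.1.1 already makes the set for listings.
- **SAP 7.5:** replace the text with a by-subject listing of ECG results with the investigator's interpretation, on the same set and in the same order.
- **SAP 7.7:** name every Protocol 8.6.4 output that is reduced to a listing or dropped outright, including PE, other medical history and non-UC medications. State whether PE changes from screening are held in the database or only in source documents or as adverse events. If they are in the database, list them.

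SAP 1.2 need not change. If the SAP is not reopened, its Introduction already provides for later changes to be documented in the synoptic report.

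The cost is two plain listings, possibly a third for PE, a few sentences, and a few extra pages in the report. The listings would be descriptive only and would support no comparison between arms.
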